#### **4.13. Connection between Primary Endpoint and Patient reported Measures, clinical assessment and frailty index**

In order to establish the interrelationship between the primary endpoints and PROs, the following analyses will be performed restricted to the placebo group. These analyses will be performed on two subgroups of the PPE set:

- participants with any RT-PCR confirmed RSV disease (see [above](#) for definition)
- participants with any ARI (see [Any ARI](#) definition, independently of RSV etiology)

For the following patient reported measures:

- AUC of the change from baseline for the Total RiiQ Respiratory and Systemic symptom score
- AUC of the change from baseline for the Total RiiQ Case Definition symptom score
- AUC of the change from baseline for the Total RiiQ Impact on Daily Activity score
- The change in IADL score between ARI Day 3-5 and baseline
- The change in augmented frailty score between baseline and end of season

The number of observations, median, first and third quartile, will be calculated for participants meeting each case definition and participants not meeting any case definition or not meeting the considered case definition; this will also be graphically depicted with boxplots.

Note: In case a participant experiences two or more ARIs during the study the same rule as for the RiiQ will be used.

As a sensitivity check the same analysis will be performed but without taking into account cough for any of the case definitions.

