## 4.6. Lawton-Brody Instrumental Activities of Daily Living (IADL) Scale

The Lawton-Brody IADL questionnaire covers 8 domains (see [Attachment 7](#)). Women are scored on all 8 domains; for men, the domains of food preparation, housekeeping, and laundering are excluded from the analysis, regardless if they are filled in. Participants are scored according to their highest level of functioning in that category (either 0 or 1). A summary score ranges from 0 (low function, dependent) to 8 (high function, independent) for women, and from 0 through 5 for men.

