### 4.6.1. Analysis Methods

For all participants with any RT-PCR-confirmed RSV disease (see [above](#) for definition) from the PPE set, descriptive statistics of the actual values and the change from baseline of the IADL score will be tabulated by sex and group for each timepoint collected.

In case two or more assessments are reported at the same day then the worst total Lawton Brody score will be used. The worst score is the smallest.

In case a participant experiences two or more ARIs during the study the same rule as for the RiiQ will be used.

Note: For outputs were only planned visits (ARI Day 3-5, ARI Day 29, End of season) are presented, the worst across the different scheduled and unscheduled visits will be presented per visit.

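### Section 4.13 summarises the raw IADL change of men and women together, although the score has 8 domains in women and 5 in men, so the case-definition comparison can partly reflect sex mix

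*SAP*

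**What the plan says.** SAP Section 4.6 gives the score a different content by sex: "Women are scored on all 8 domains; for men, the domains of food preparation, housekeeping, and laundering are excluded from the analysis". The range follows: "A summary score ranges from 0 (low function, dependent) to 8 (high function, independent) for women, and from 0 through 5 for men". Attachment 7 repeats these ranges.

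Wherever else the SAP analyses the score, it allows for this:

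- Section 4.6.1, for participants with RT-PCR-confirmed RSV disease: "the change from baseline of the IADL score will be tabulated by sex and group for each timepoint collected".
- Section 5.6.1 again tabulates the actual values by sex and group.
- Section 4.7 divides the score by 8 for women and by 5 for men inside the frailty index and the augmented frailty index.

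Section 4.13 uses the score once more, as "The change in IADL score between ARI Day 3-5 and baseline". On the population it says that "the following analyses will be performed restricted to the placebo group", in two subgroups of the PPE set: participants with any RT-PCR-confirmed RSV disease, and participants with any ARI whatever its cause. The summary is the number of observations, median and quartiles, with boxplots. These "will be calculated for participants meeting each case definition and participants not meeting any case definition or not meeting the considered case definition". The section mentions no split by sex and no rescaling, and it does not refer back to Section 4.6.1. The only rule it takes from elsewhere is the RiiQ rule for participants with more than one ARI.

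**The concern.** Section 4.13 is meant to show whether meeting a primary case definition goes with a loss of function. Case-definition groups are formed after randomisation by what happened to the participant, so nothing in the design balances sex between them. A woman has eight points to lose and a man five. If the group that meets a definition contains more women than the group that does not, its raw IADL change can look worse with the same degree of deterioration. With the opposite imbalance, a true difference can look smaller than it is.

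The other four measures in the list do not carry this problem to the same degree. The three RiiQ AUCs use the same items in both sexes, and the augmented frailty index has sex-specific terms for IADL. The IADL change is the one entry in which two scales are mixed.

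**Working it through.** **The plan's own figures.** Attachment 7 lists domains A to H, which is 8. Removing food preparation, housekeeping and laundry leaves 8 - 3 = 5. The ranges 0-8 and 0-5 in Section 4.6 are reproduced.

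**Assumptions, none of them from the SAP.** Every participant is at the maximum at baseline. Each scored domain is lost independently with the same probability q in both sexes. The share of women in a case-definition group is w. The SAP gives neither q nor w, so both are varied.

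**Mean loss.** Women 8q, men 5q, ratio 8/5 = 1.6. Pooled mean = w x 8q + (1 - w) x 5q.

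- q = 0.1: w = 0.3 gives 0.3 x 0.8 + 0.7 x 0.5 = 0.59; w = 0.7 gives 0.7 x 0.8 + 0.3 x 0.5 = 0.71.
- q = 0.4: w = 0.3 gives 0.3 x 3.2 + 0.7 x 2.0 = 2.36; w = 0.7 gives 0.7 x 3.2 + 0.3 x 2.0 = 2.84.

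**Median and quartiles, which are what Section 4.13 reports.** These come from the mixture of Binomial(8, q) with weight w and Binomial(5, q) with weight 1 - w. For example, at q = 0.1 the probability of no loss is 0.9^8 = 0.430 in women and 0.9^5 = 0.590 in men. The pooled probability of no loss is 0.3 x 0.430 + 0.7 x 0.590 = 0.542 at w = 0.3, so the median is 0. At w = 0.7 it is 0.7 x 0.430 + 0.3 x 0.590 = 0.478, so the median is 1.

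| q | Q1, median, Q3 of loss at 30% women | at 70% women |
|---|---|---|
| 0.05 | 0, 0, 1 | 0, 0, 1 |
| 0.10 | 0, 0, 1 | 0, 1, 1 |
| 0.15 | 0, 1, 1 | 0, 1, 2 |
| 0.20 | 0, 1, 2 | 1, 1, 2 |
| 0.30 | 1, 2, 2 | 1, 2, 3 |
| 0.40 | 1, 2, 3 | 2, 3, 4 |

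Deterioration per domain is identical along each row, so every shift is due to sex mix alone. The median moves by one point at q = 0.1 and q = 0.4. Only one quartile moves at q = 0.15 to 0.3, and nothing moves at q = 0.05.

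**Where imbalance is likelier.** By chance alone, the SD of the difference in female share between two groups of n1 and n2 is sqrt(p(1 - p)(1/n1 + 1/n2)), with p the overall share of women, so it falls as the groups grow. The any-ARI subgroup contains the RSV-confirmed cases, so chance imbalance matters more in the RSV-confirmed subgroup. If women are more or less likely than men to meet a definition, that imbalance stays in both subgroups whatever their size.

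**The case against.** Four points can be made in defence of the plan.

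First, Section 4.13 never says that the sexes are pooled, and the Introduction leaves table layouts to separate data presentation specifications, where a split could be added. That is true. But the section names its comparison groups and sex is not among them, whereas Sections 4.6.1 and 5.6.1 state the split outright. Followed as written, it gives one summary over both sexes.

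Second, the measure is a within-person change, so the sex difference in baseline level cancels. That also stands. What remains is a different sensitivity to loss, and it matters only if enough domains are lost and the sex mix differs between the groups.

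Third, Section 4.6.1 already shows the change by sex. It does so by vaccine group and for RSV-confirmed cases only. It does not compare case-definition groups and does not cover any ARI.

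Fourth, little depends on the result: one of five descriptive measures, in placebo participants, with no test or confidence interval attached. The season two and three counterpart in Section 5.12 does not use IADL. This stands in full and limits the weight of the point.

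A reader might also go further and infer that the three domains scored only in women are the ones an ill person loses most easily, which would make the distortion much larger than 1.6. Attachment 7 does not support that. Housekeeping still scores 1 for someone who needs help with every task, laundry still scores 1 for washing small items, and easily lost domains such as shopping are shared by both sexes.

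**Conclusion.** The point holds and is minor. The comparison of IADL change in Section 4.13 mixes a 0-8 and a 0-5 scale across non-randomised groups, and it is the only IADL analysis in the SAP without a split by sex or a sex-specific divisor. Under equal per-domain loss the expected raw loss differs by a factor of 1.6. A large contrast in sex mix (30% against 70% women) moves the reported median by at most one point over the values of q tried, and at low q moves nothing. These sizes rest on the assumed q, independent losses, a baseline at the maximum and the assumed shares of women.

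A reader might infer that an observed difference between case-definition groups is likely to be wholly a product of sex mix, or that the analysis rests on a handful of RSV cases. The SAP supports neither. It gives no group sizes or sex shares for this analysis, and it also runs the comparison in the larger any-ARI placebo subgroup. What can be said is that the comparison can partly reflect sex mix, more so in the RSV-confirmed subgroup. The efficacy analyses and the proof-of-concept decision are not affected.

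**What to change.** In Section 4.13, state that the IADL change is presented by sex, in line with Sections 4.6.1 and 5.6.1. Two alternatives keep one summary for both sexes:

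- Compute the change in both sexes on the five shared domains. This puts everyone on one scale but discards three domains in women.
- Express the change as a proportion of the sex-specific maximum, 8 or 5. Under the assumption above, the expected proportion lost is then q in both sexes. The median can still move a little, because the steps are 1/8 in women and 1/5 in men. At q = 0.1 and 70% women, 0.478 of participants lose nothing, and a further 0.7 x 8 x 0.1 x 0.9^7 = 0.268 lose one eighth. The median proportion is therefore 0.125, against 0 at 30% women.

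The split by sex is the simplest choice and the closest to the rest of the SAP. It costs one line of text and one more stratification in the table and boxplots, needs no new data, and changes no endpoint. The downside is smaller cells, chiefly in the RSV-confirmed subgroup; Section 4.6.1 already accepts this.

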#### 4.14. Viral Load

For RSV A viral load, RSV B viral load and their combination, descriptive statistics for ARI Day 1-2, ARI Day 3-5 and for the maximum viral loads observed between the 2 visits, will be calculated for participants with any RT-PCR-confirmed RSV disease and for participants fulfilling the 3 case definitions, by group. The difference and 95% CI of the maximum log10 viral loads between the 2 groups will also be calculated.

For analysis purposes, the qRT-PCR viral load will be imputed with the midpoint on the log scale between the limit of detection (LOD) and LLOQ of the RSV qRT-PCR assay when the result is ‘target detected’ (TD) but non-quantifiable.

- For the RSV-A qRT-PCR assay, the LOD is 620 copies/mL and the LLOQ is 1000 copies/mL, a result that is TD will be imputed with 2.90 log10 copies/mL.
- For the RSV-B qRT-PCR assay, the LOD is 80 copies/mL and the LLOQ is 250 copies/mL, a result that is TD will be imputed with 2.15 log10 copies/mL.

When the result is ‘target not detected’ (TND) (meaning below the LOD), for both RSV A and RSV B the value of TND will be imputed with the respective LODs.

In case of co-infection with both subtypes RSV A and B, the rules below will be applied for the overall analyses of viral load from the time the co-infection is detected (i.e. result of TD or >LLOQ), [Table 12](#):

- In case of two quantifiable results: the log10 of the sum of the RSV A and RSV B results in copies/mL will be used.
- In case of a quantifiable result and a TD/TND result: use the imputed TD/TND on the copies/mL scale value and then use the log10 of the sum of the imputed value and the quantifiable result
- In case of two TD results, or one TD and one TND result: use the imputed TD/TND on the copies/mL scale values and then use the log10 of the sum of the imputed values
- In case of two TND results: the log10 of the sum of the RSV A LOD and RSV B LOD results in copies/mL will be used.

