### **5.13. Viral Load**

Viral loads will be analyzed similar to season one (see Section 4.14) for participants with any RT-PCR-confirmed RSV disease and for participants fulfilling Case Definition 1, during the second or third RSV season and across the three RSV seasons.

The viral load analysis will be conducted separately for RSV A and RSV B infected participants. The overall RSV viral loads will not be calculated.

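### Season 1 RSV A and RSV B viral-load tables (SAP Section 4.14) include, as written, participants infected only with the other subtype at the LOD, which dilutes the group difference and exposes it to subtype mix

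*SAP*

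**What the plan says.** Section 4.14 opens: "For RSV A viral load, RSV B viral load and their combination, descriptive statistics for ARI Day 1-2, ARI Day 3-5" and for the maximum over the two visits. These summaries "will be calculated for participants with any RT-PCR-confirmed RSV disease and for participants fulfilling the 3 case definitions, by group". The difference, with 95% CI, in maximum log10 "viral loads between the 2 groups will also be calculated".

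The imputation rules are:

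- Detected but not quantifiable (TD), RSV A: "the LOD is 620 copies/mL and the LLOQ is 1000 copies/mL, a result that is TD will be imputed with 2.90" log10 copies/mL.
- Detected but not quantifiable (TD), RSV B: "the LOD is 80 copies/mL and the LLOQ is 250 copies/mL, a result that is TD will be imputed with 2.15" log10 copies/mL.
- Target not detected (TND): "for both RSV A and RSV B the value of TND will be imputed with the respective LODs".
- Combination: "In case of co-infection with both subtypes RSV A and B, the rules below will be applied for the overall analyses of viral load", with the sums set out in Table 12.

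The population is not specific to a subtype. Under Section 4.4.3.1, RSV confirmation rests on GeneXpert, and Attachment 3 lists RSV without subtype for that panel.

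For seasons two and three and across the three seasons, Section 5.13 sets a different rule: "The viral load analysis will be conducted separately for RSV A and RSV B infected participants". It also drops the overall load.

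**The concern.** A participant with RSV B alone has no RSV A to quantify. Entering that participant in the RSV A table at the RSV A LOD records the absence of one virus as a low load of it. The RSV A mean over all RSV cases then depends on two things: the load in those who have RSV A, and the share of cases that are RSV A.

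Two consequences follow for the subtype-specific differences.

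- **Dilution.** Whenever both subtypes circulate, a true difference in load shrinks, because part of each group sits at a fixed value.
- **Subtype-mix bias.** If the share of RSV A cases differs between groups, the tables show a difference even when loads among infected participants are equal. Cases are selected after randomisation, so randomisation does not balance their subtype mix. Efficacy that differs by subtype would shift it systematically.

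Season 1 subtype tables would also not be comparable with those produced under Section 5.13.

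**Working it through.** **The plan's own figures.** The TD value is the midpoint of LOD and LLOQ on the log10 scale.

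- RSV A: (log10 620 + log10 1000)/2 = (2.792 + 3.000)/2 = 2.896, stated as 2.90.
- RSV B: (log10 80 + log10 250)/2 = (1.903 + 2.398)/2 = 2.151, stated as 2.15.

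Both reproduce. The TND values are log10 620 = 2.79 and log10 80 = 1.90.

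**Assumed inputs.** The SAP gives no subtype shares, mean loads, SDs or case counts. The working assumes mean loads of 5 to 7 log10 in infected participants, several subtype shares, and no co-infection.

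**Formula.** With p the share of cases with the subtype, m their mean load and L the log10 LOD, the group mean over all RSV cases is p·m + (1 − p)·L.

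**Dilution.** With the same p in both groups and a true difference d, the reported difference is p·d. At p = 0.5, a true 1.0 log10 becomes 0.5 and a true 0.7 becomes 0.35. The spread grows as well: with mean 6 and within-subtype SD 1.5, the mixture SD is sqrt(0.5 × 1.5² + 0.25 × (6 − 2.79)²) = 1.92.

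**Subtype mix, no true effect.** The artefact is (difference in share) × (m − L).

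| RSV A share by group | Table | m = 5 | m = 6 | m = 7 |
|---|---|---|---|---|
| 50% v 60% | RSV A | 0.22 | 0.32 | 0.42 |
| 50% v 60% | RSV B | 0.31 | 0.41 | 0.51 |
| 40% v 60% | RSV A | 0.44 | 0.64 | 0.84 |
| 40% v 60% | RSV B | 0.62 | 0.82 | 1.02 |

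The RSV A and RSV B artefacts have opposite signs.

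**Masking.** Take RSV A shares of 60% (vaccine) and 40% (placebo), a placebo mean of 6 and a true reduction of 1.0. The RSV A difference is (0.6 × 5 + 0.4 × 2.79) − (0.4 × 6 + 0.6 × 2.79) = +0.04, so the reduction disappears.

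**Confidence intervals.** This was simulated with 4,000 trials per scenario, Welch intervals, an assumed 30 vaccine and 90 placebo cases, mean 6, SD 1.2 and no true difference.

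| RSV A share, vaccine v placebo | CI excludes 0, all RSV cases | CI excludes 0, RSV A cases only |
|---|---|---|
| 50% v 50% | 5.3% | 5.0% |
| 40% v 60% | 41% | 5.8% |
| 30% v 60% | 74% | 5.4% |

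**Combined load.** Even if Table 12 were applied to a case with a single subtype, adding 620 copies/mL to 10^6 gives log10(1,000,620) = 6.0003. The LOD contributes almost nothing.

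**The case against.** Several points on the other side are fair.

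- **A milder reading exists.** The LOD rule says how an undetected value is imputed, not who belongs in each subtype table. It could be meant only for negative visits of a participant who has that subtype. Section 4.14 does not say so, however, and its summing rules are limited to co-infection while the TND rule carries no limit. Two programmers could produce different tables, so the text needs fixing under either reading.
- **Not every viral-load difference is affected.** A reader might infer that all season 1 viral-load comparisons are distorted. The combined load is also planned and is practically free of the artefact.
- **A false difference is not inevitable.** A reader might infer bias in any case. If expected subtype shares are equal, chance imbalance is part of the sampling variation that the CI covers, as the 5.3% shows. Systematic bias requires shares that differ between groups. Dilution does not.
- **Season 1 cases are not left out altogether.** Section 5.13 covers the analysis across three seasons, which includes them. Only the stand-alone season 1 subtype tables remain open.
- **Undetected results are not always uninformative.** A GeneXpert-positive participant may be TND on both quantitative assays, and that may be a truly low load. A bare restriction to detected cases would drop such participants and could select on the outcome.
- **Consequence is limited.** Viral load carries no hypothesis or alpha and plays no part in proof of concept.

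**Conclusion.** The point holds for the stand-alone season 1 RSV A and RSV B summaries and their between-group differences, taking Section 4.14 as written. Dilution follows whenever both subtypes occur. Its size is the share of cases with the other subtype, so half the true difference is lost at an assumed 50%. Subtype-mix bias depends on shares differing between groups; for RSV A at 50% versus 60% it is 0.22 to 0.42 log10 at assumed means of 5 to 7. The sizes rest on these assumptions; the mechanism does not.

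The documents do not support extending the point to the combined load, to the analysis across seasons, or to the primary conclusions. It is a worthwhile correction to a descriptive analysis, and the SAP's own Section 5.13 shows the way.

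**What to change.** Section 1.6 shows that the season 1 primary analysis has been done, so leave Section 4.14 as the record and add a post-hoc season 1 analysis in Section 4.17:

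1. Analyse each subtype's load (both visits, maximum, and group difference with CI) only in participants infected with that subtype, as in Section 5.13.
2. Apply TND-to-LOD for a subtype only to negative visits of a participant infected with that subtype.
3. Report case counts by subtype and group beside the tables.
4. Count by group the GeneXpert-positive participants who are TND on both quantitative assays. Keep them in the combined load at the imputed LODs, log10(620 + 80) = 2.85, and examine them in a sensitivity analysis, so that the restriction does not silently select on low load.

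The cost is fewer participants in each subtype table and a small amount of extra programming.

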**Table 12: Rules for coinfections**

RSV A	RSV B	Combination
VL value	VL value	VL (RSV A) + VL (RSV B) in copies/ml
VL value	TD	VL (RSV A) + 10 2.15 copies/ml
TD	VL value	10 2.90 copies/mL + VL (RSV B)
VL value	TND	VL (RSV A) + 80 copies/mL (LOD of RSV B)
TND	VL value	620 copies/mL (LOD of RSV A) + VL (RSV B)
TD	TD	10 2.90 copies/mL + 10 2.15 copies/mL
TND	TND	620 copies/mL (LOD of RSV A) +80 copies/mL (LOD of RSV B)
TND	TD	620 copies/mL (LOD of RSV A) + 10 2.15 copies/mL
TD	TND	10 2.90 copies/mL + 80 copies/mL

VL: viral load; TD: target detected; TND: target not detected

Note: Log10 transformation should occur after making the sums.

#### 4.15. Approximate ARI surveillance compliance

Participants will receive an ARI surveillance question twice per week questioning whether they have experienced any cold or respiratory infection symptoms. The responsiveness of the participants to this ARI surveillance question will be summarized for both groups.

The approximate number of ARI surveillance questions that each participant is expected to have responded between vaccination (inclusive) and the end of the ARI surveillance or the day of discontinuation (in case of early discontinuation) will be calculated as follows:

1. First the number of weeks between day of vaccination and the end of the ARI surveillance (20th March 2020) or day of discontinuation (in case of early discontinuation) will be calculated.
2. Then the number of weeks that the participant experienced an ARI episode, will be calculated.
3. And finally, the difference of the two (1-2) will be multiplied by 2, since for each week a participant is part of the ARI surveillance journey, we expect to have responses in 2 questionnaires.

For estimating the percentage of compliance per subjects the number of ARI surveillance questions answered after vaccination, until the end of the ARI surveillance period and outside RSV-episodes will be divided by the number obtained in step 3 and will be multiplied by 100.

Note: In case multiple ARI surveillance questions have been answered at the same day, only one will be used.

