#### **4.4.3. Major Secondary Endpoints**

##### **4.4.3.1. Definition**

First occurrence of a considered endpoint is defined as the first day of symptoms of the first ARI episode where the criteria for the respective endpoint are fulfilled on at least one assessment of the considered episode. The secondary objectives are defined as follows:

- **First occurrence of any RT-PCR-confirmed RSV ARI**

This is defined as any acute respiratory infection (ARI) in combination with RSV confirmation by RT-PCR in at least one of the samples taken up to 7 days after the onset of the ARI episode or during the ARI episode, see Section 4.4.2.1.2.

**Any ARI** is defined as new onset or worsening of any of the LRTI and URTI clinical symptoms. Systemic symptoms will not be taken into account. New onset or worsening of symptoms is

determined in a similar way as for the primary endpoint (Section 4.4.2.1.1). Table 8 contains the LRTI and URTI symptoms collected in the RiiQ and the clinical assessment.

ARIs indicated by the site as being initiated in error by the participant, with no RT-PCR swab linked to them will not be taken into account in the analysis.

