#### **5.14. Approximate ARI surveillance compliance**

The responsiveness of the participants to the ARI surveillance question will be summarized for both groups, for the second and third RSV season, similar to the first RSV season. A summary might be added across the three RSV seasons. For details, refer to Section 4.15. For the second RSV season, however, the number of weeks between the Day 365 visit and the end of the ARI surveillance (Day 730a) or day of discontinuation (in case of early discontinuation) will be used in step 1. A similar calculation will be done for the third RSV season based on the Day 730 visit and the end of the ARI surveillance (15th April 2022). Note: in case an ARI episode extends over multiple seasons, the respective duration in the considered season is taken into account for the calculations. Note that as ARI surveillance during the 1st season was stopped at 20 March 2020, for ARIs during the 1st Season, only the duration up to 20 March should be taken into account for the calculation of the approximate ARI surveillance.

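### The ARI surveillance compliance formula removes all ARI weeks from the expected questions but only RSV-episode answers from the answered ones, so compliance can be inflated and can exceed 100%.

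*SAP*

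**What the plan says.** SAP Section 4.15 opens with the schedule: "Participants will receive an ARI surveillance question twice per week questioning whether they have experienced any cold or respiratory infection symptoms". The expected number of answers is built in three steps:

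- Step 1: "First the number of weeks between day of vaccination and the end of the ARI surveillance" (20 March 2020), or to discontinuation if earlier.
- Step 2: "Then the number of weeks that the participant experienced an ARI episode, will be calculated". There is no condition on the RT-PCR result.
- Step 3: "And finally, the difference of the two (1-2) will be multiplied by 2".

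The percentage then takes the answers given after vaccination, "until the end of the ARI surveillance period and outside RSV-episodes will be divided by the number obtained in step 3". One further rule limits the numerator: "In case multiple ARI surveillance questions have been answered at the same day, only one will be used".

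Elsewhere the SAP keeps the two kinds of episode apart. In Section 4.4.3.1, any ARI "is defined as new onset or worsening of any of the LRTI and URTI clinical symptoms", while an RSV ARI also needs RT-PCR confirmation.

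Section 5.14 summarises responsiveness in the second and third seasons "similar to the first RSV season". It changes the start and end dates and refers back to Section 4.15 for the rest.

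**The concern.** The numerator and denominator of a compliance percentage should cover the same time. Here they do not. The weeks of a non-RSV ARI leave the denominator, but any surveillance answers dated within those weeks stay in the numerator. The same happens for an ARI with no usable RT-PCR result, since it is an ARI but not a confirmed RSV episode.

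The error can only push the figure up. The table could then show impossible values above 100%. Less visibly, it could let answers given during an ARI offset questions missed at other times. Because the twice-weekly question is how symptoms of a possible ARI are monitored (Section 1.2), a reader may look to this table for how well participants responded.

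**Working it through.** The SAP gives no compliance figure for this rule, so there is none to reproduce.

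**Inputs from the SAP.** Two questions per week; all ARI weeks removed in step 2; RSV-episode answers alone removed from the numerator; at most one answer counted per day. There is no cap at two answers per week or at 100%.

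**Assumed inputs.** W = 18 surveillance weeks and one non-RSV ARI of A = 3 weeks. The number k of surveillance answers dated within that ARI runs from 0 to 6.

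**Formulas.** Let n be the number of answers given outside any ARI.

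- Expected questions = 2 × (W − A) = 2 × (18 − 3) = 30.
- Compliance as written = 100 × (n + k) / 30.
- Compliance with matching exclusions = 100 × n / 30.
- Overstatement = 100 × k / 30 points, which is never negative.

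**Results as written.**

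| Answered outside the ARI | Matching rule | k = 0 | k = 1 | k = 2 | k = 6 |
|---|---|---|---|---|---|
| 30 of 30 | 100% | 100% | 103.3% | 106.7% | 120% |
| 27 of 30 | 90% | 90% | 93.3% | 96.7% | 110% |
| 24 of 30 | 80% | 80% | 83.3% | 86.7% | 100% |

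The last cell shows the masking: six questions missed outside the ARI are offset by six answers inside it, and 80% is reported as 100%.

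**Other assumed lengths of surveillance, same 3-week ARI, full responder.** With W = 20, 34 questions are expected: one answer inside gives 35/34 = 102.9% and all six give 40/34 = 117.6%. With W = 24, 42 are expected: 43/42 = 102.4% and 48/42 = 114.3%.

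**Season 2.** Section 5.14 runs from Day 365 to Day 730, that is 365/7 = 52.1 weeks. Expected questions are 2 × (52.1 − 3) ≈ 98, so one answer inside the ARI adds 1/98 ≈ 1.0 point and six add 6/98 ≈ 6.1 points.

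**Can answers fall inside an ARI window?** Section 4.4.2.1.3 derives the window afterwards. Its start is the date in the CE domain, even if diary symptoms came later, and its end is the last day with symptoms above baseline. Section 4.4.3.1 counts days with missing symptom assessments as part of the episode. The window is therefore not the same as the device's status on the day.

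**Ceiling on an arm difference.** Take the SAP's planning values of 0.75% incidence and 70% VE (Table 4), and 2,900 per group. Placebo cases: 2,900 × 0.0075 = 21.75. Active cases: 21.75 × 0.30 = 6.5. The difference is about 15 participants, or 15/2,900 ≈ 0.5% of an arm. Even at 20 points for each of them, the shift in an arm's mean is 0.005 × 20 ≈ 0.1 point. If all RSV ARIs were three times as common (assumed), it is about 0.3 point.

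**The case against.** The best defence is that no surveillance questions are put during an ARI. Step 3 expects two answers for each week a participant is in the surveillance journey, and Section 4.4.2.1.1 has participants report symptoms daily on the RiiQ during an episode. If nothing is answered inside an ARI, the mismatch has no effect. The SAP does not say that the questions stop, however, and an exclusion of answers inside episodes would be needless if none could exist. The derived windows also leave room for stray answers at the edges. The defence limits the likely size but does not remove the error.

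A second defence is that the section calls itself approximate, that the added notes in Section 5.14 speak only of ARI episodes, and that its footnote cuts weeks, episodes and answers at the same relative Day 730. The intent is plainly to align them, so *RSV-episodes* is probably a slip for *ARI episodes*. That is a fair reading of intent. But an approximate week count does not explain different episode sets above and below the line, and a programmer who follows the text would implement the slip.

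It also stands that 120% is the extreme of the example: every question would have to be sent and answered throughout a 3-week illness. One or two stray answers, giving about 103% to 107%, are a more plausible leak.

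**Conclusion.** The mismatch is in the text and its direction is certain. Its size is not: it runs from zero, if no answers fall inside non-RSV ARI windows, to 20 points for an affected participant in the 18-week, 3-week-ARI example. Surveillance length, ARI length and answers inside the ARI are all assumed. Participants without a non-RSV ARI are unaffected. This is a minor wording error in a descriptive summary.

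A reader might infer three stronger things that the SAP does not support:

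- *Reported compliance is in fact too high.* That needs answers inside non-RSV ARIs, and the SAP does not say how many there are.
- *The rule biases the comparison between arms, because the exclusion depends on RSV status.* Confirmed RSV episodes are treated consistently, since both their weeks and their answers are removed. If non-RSV ARIs are balanced, the inflation is similar in both arms, and the ceiling above is about 0.1 to 0.3 point.
- *Vaccine efficacy is affected.* The efficacy set (Section 2.3.3), the imputation model (Section 4.4.1.2) and the primary model with its follow-up offset (Section 4.4.2.2) do not use compliance. Section 4.15 says only that responsiveness is summarised by group.

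**What to change.** In SAP Section 4.15, replace *outside RSV-episodes* by *outside ARI episodes*, so that numerator and denominator exclude the same episodes. Section 5.14 inherits the change by reference and needs no edit of its own.

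The cost is one word and a rerun of the descriptive compliance summaries. If the program already excludes answers in all ARI episodes, a note saying so is enough.

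The change does not guarantee values of 100% or less. The week count is approximate and the only cap is one answer per day, so small excesses may remain.
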